4.4.1. Baseline

For the purpose of the statistical analysis, Baseline is defined as the last visit prior to and including date of the randomization visit (V2 – Day 1). Unless otherwise specified, baseline values are defined as the measurements taken during this visit. In case of multiple measurements

during baseline visit, the last assessment will be considered as the baseline evaluation. In case of missing value at baseline visit, but availability of other values collected before the first administration of the IMP (e.g. at Screening), the last available value collected will be used as the baseline value.

4.5. Handling of Missing Data

Data will be presented in the listings as reported. For summaries and analysis, the conventions described in the following paragraphs apply.

4.5.1. SANDE Global Score

For the efficacy inferential analysis, missing SANDE Global Score data will be imputed using the imputation methods described in [Section 8.1.1](#) and [Section 8.1.2](#). Descriptive analyses will be based on observed data.

4.5.2. Key Secondary and Secondary Endpoints

For the efficacy inferential analysis, missing data on key secondary and secondary endpoints will be imputed using the imputation methods described in [Section 8.2.1.2](#) or [Section 8.2.1.3](#), depending on the nature of the data. Descriptive analyses will be based on observed data.

4.5.3. Adverse Event Data

Algorithm to impute partial or missing end dates is described in [Appendix 13.2](#), but partially or missing AE start dates will not be imputed. The rule for the classification of AEs and TEAEs is also shown in [Appendix 13.2](#) with details on the derivation of the period for TEAEs after date imputation.

In case one or more AE characteristics are missing (for example severity and relationship to study drug), the most conservative approach will be taken (in the example, the AE will be considered severe, and drug related).

In listings of AE data, the partial dates as collected will be displayed. Imputed dates with details of what has been imputed in brackets (e.g. D if day is imputed, M if month, DM if both) will be provided.

4.5.4. Prior/Concomitant Medication and Procedure Data

Algorithm to impute partial or missing end dates is described in [Appendix 13.2](#), but partially or missing medication/procedure start dates will not be imputed. The rule for the classification in “prior” or “concomitant” medication/procedure is also shown in [Appendix 13.2](#).

In listings of concomitant medication and procedure data, the partial dates as collected will be displayed. Imputed dates with details of what has been imputed in brackets (e.g. D if day is imputed, M if month, DM if both) will be provided.

5. Patient Disposition

5.1. Disposition

The number of patients who were screened, and the eligibility criteria met/failed will be summarized based on all screened patients. The number and percentage of screen failure patients will be summarized for each exclusion criteria met and/or inclusion criteria failed.

Disposition of all randomized patients will be summarized by treatment group including:

- Full Analysis Set
- Safety Set
- Per-Protocol Set
- Number of patients who completed the study treatment
- Number of patients who prematurely discontinued the study treatment
 - Number of patients who prematurely discontinued the study treatment but complete the study
 - Number of patients who prematurely discontinued the study treatment and discontinued the study
- Primary reason for treatment discontinuation
- Number of patients who completed the study
- Number of patients who prematurely discontinued the study (early termination)
- Primary reason for study discontinuation.
- Number of patients who were unblinded during the study and the reason (Emergency situation, Other).

Primary reasons for treatment discontinuation collected on the eCRF will be summarized with the following categories separately:

- Adverse Event
- Death
- Lost to Follow-up
- Physician Decision
- Protocol Deviation
- Withdrawal by Patient
- Pregnancy
- Treatment Discontinuation due to Tolerability Issues
- Other

Primary reasons for study discontinuation collected on the eCRF will be summarized with the following categories separately:

- Adverse Event
- Death
- Lost to Follow-up
- Physician Decision
- Protocol Deviation
- Screen Failure
- Study Terminated by Sponsor
- Withdrawal by Patient
- Other

The distribution of the time from randomization to study discontinuation will also be summarized using time-to-event analysis. A log-rank test will be used to compare distributions among the three groups (two IMP groups and the Vehicle group).

Screening data will be listed by patients as collected based on all screened patients (SCR). Disposition data will be listed by patients as collected based on all randomized patients (RND) by site.

Inclusion and exclusion criteria deviations will be presented for all screened patients in a data listing by site.

In addition, total study duration from the screening (date of informed consent) to the last visit of each patient will be summarized.

5.2. Protocol Deviations

Protocol deviations (PDs) that will be analyzed and reported in the TLFs come from two different sources: CTMS and SAS programming. All PDs will be reviewed in a masked manner before the hard lock of the database in order to check the ones that actually have an impact (e.g. bias) on the statistical analysis. PDs will be classified for analysis purposes in Major and Minor PDs according to the level of bias that they can produce on the primary and/or key secondary endpoints. Not all deviations reported in the CTMS will be analyzed (i.e. will not be classified as either major or minor PDs), if not relevant from an analysis perspective. Major PDs will define patients that will be excluded from the PP set.

Major protocol deviations derived in SAS:

The following PDs will be derived in SAS and classified as major. Any further change, if any, will be discussed and documented during the blind DRM.

- Lack of compliance with IMP (compliance <80% or compliance >120%).
- Exposure to IMP lower than expected (exposure in days < 24 days).
- Missing all post-baseline assessments for one or more of the primary and key secondary endpoints (subjects should have at least one post-baseline assessment for each of the primary and key secondary endpoints).
- Intake of prohibited medications.

Minor protocol deviations derived in SAS:

- Lack of compliance with NIMP (compliance <80% or compliance >120%).

Finally, number of patients with at least one major/minor PD will be summarized. Major PD will be tabulated, while all PDs (major and minor) will be listed, including full description and the GCP severity classification, as reported in the PD rule document (significant / not significant). Tabulation and listing will be based on all randomized patients.

6. Demographics and Baseline Characteristics

6.1. Demographics and Baseline Characteristics

Demographic and baseline characteristics data to be analyzed will include age, sex, race, ethnicity, childbearing potential, based on the FAS accordingly to the planned treatment.

Descriptive statistics will be calculated for the following continuous variables:

- Age (years)

Number and percentage of patients will be provided for the following categorical variables:

- Sex (Male, Female)
- Race (White, Black or African American, Asian, American Indian or Alaska Native, Native Hawaiian or Other Pacific Islander, Other, Multiple, Not Reported, Unknown)
- Ethnicity (Hispanic or Latino, Not Hispanic or Latino, Not Reported, Unknown)
- Childbearing Potential (Yes, No, Not Applicable)
- Region (US, EU)
- Study Eye (Right Eye, Left Eye).

6.2. Medical History

Medical history will be summarized based on the SAF according to the actual treatment received by condition type (history condition / concomitant condition). Medical history will be coded according to latest version of Medical Drug Regulatory Activities (MedDRA) and will be summarized by body system code and preferred term (PT), with body system code sorted alphabetically and PTs within each body system code in descending order of frequency.

Patients experiencing more than one disease will be counted only once within each SOC and PT.

Ophthalmic medical history will be summarized separately from non-ophthalmic medical history. Ophthalmic medical history will be summarized for the Study Eye and fellow eye separately.

A by-patient listing of ophthalmic and non-ophthalmic medical histories will be presented and ordered by site. Ongoing conditions will be considered as “concomitant conditions” and will be denoted in the listing. Any conditions with end dates on or after screening visit or with missing end dates will also be considered as “concomitant conditions”.

6.3. Dry Eye History

Dry eye history will be summarized by eye (study eye and fellow eye) for time from diagnosis (years), cause of dry eye, receiving of prior treatment, and eye affected by moderate to severe dry eye. Time from diagnosis will be calculated by date of informed consent – date of diagnosis for each eye + 1, then divided by 365.25. Partial dates are treated according to below rules:

- if month and day are missing, set to 01-July of that year;
- if only day is missing, set to 15th of that month.

Dry eye history will be presented in a by-patient listing by site as collected per eCRF.

7. Treatments, Medications, and Procedures

7.1. Prior and Concomitant Medications

Prior and concomitant medications will be coded using the latest version of World Health Organization Drug Dictionary (WHODrug) during the study.

Ophthalmic and non-ophthalmic medications (both prior and concomitant) will be summarized based on the FAS, sorted by alphabetical order of Anatomical Therapeutic Chemical 4 (ATC4) level, and then descending frequencies of preferred term. If ATC4 level is missing, the last available level will be used.

By-patient listings of prior and concomitant medications will be presented.

Partial missing start or end dates will be imputed as described in [Appendix 13.2](#) for medications analysis.

7.1.1. Prior Medications

Prior medications are defined as medications that stop before the first dose of study drug.

Ophthalmic prior medications will be summarized separately from non-ophthalmic prior medications. Ophthalmic prior medications will be summarized for the study eye and fellow eye separately. Medications will be sorted by alphabetical order of ATC4 level, and then descending frequencies of preferred term. If ATC4 level is missing, the last available level will be used.

7.1.2. Concomitant Medications

Concomitant medications are defined as medications first received at or after the first dose of study drug, medications received before first dose of study drug and continued after first dose, or medications with missing stop date.

Ophthalmic concomitant medications will be summarized separately from non-ophthalmic concomitant medications. Ophthalmic concomitant medications will be summarized for the study eye and fellow eye separately.

7.1.3. Prohibited Medications

During the whole period of the participation to the trial (about 10 weeks) patients should not use ophthalmic steroids, ophthalmic immunomodulators such as cyclosporine A and lifitegrast, intranasal tear-secretagogues such as varenicline, ophthalmic topical anti-histamine, any derivatives of nerve growth factor, or any medications as part of another clinical trial. The use of

artificial tears - lubricating CCI not provided by the Sponsor is also forbidden. Patients should not use punctal plugs, contact lenses (including scleral lenses), moisture goggles, warm compresses or electro/magnetic stimulation devices on the eye, face or scalp.

The algorithm for the identification of the prohibited medications taken during the study has been reported in [Appendix 13.4](#).

Before the study unmasking, a masked review of the concomitant medications taken by the patients during the study will be done in order to verify the presence of prohibited medications; their frequency and dosage will also be considered in order to define the severity of the deviation.

Prohibited medications will be summarized based on FAS according to the planned treatment. Ophthalmic prohibited medications will be summarized separately from non-ophthalmic prohibited medications. Ophthalmic prohibited medications will be summarized for the study eye and fellow eye separately.

A by-patient listing of prohibited medications will be presented by treatment.

7.2. Prior and Concomitant Procedures

Prior and concomitant procedures will be coded using the latest version of MedDRA during the study. Ophthalmic and non-ophthalmic procedures will be summarized based on the FAS according to the planned treatment, sorted by system organ class (SOC) and PT, with SOC's sorted alphabetically and PTs within each SOC in descending order of frequency.

By-patient listings of prior and concomitant ophthalmic and non-ophthalmic procedures will be presented by site.

Partial missing start or end dates will be imputed as described in [Appendix 13.2](#) for medications analysis.

7.2.1. Prior Procedures

Prior procedures are defined as procedures that stop before the first dose of study drug.

Ophthalmic prior procedures will be summarized separately from non-ophthalmic prior procedures. Ophthalmic prior procedures will be summarized for the study eye and fellow eye separately.

7.2.2. Concomitant Procedures

Concomitant procedures are defined as procedures first received at or after the first dose of study drug, procedures received before first dose of study drug and continued after first dose or procedures with missing stop date.

Ophthalmic concomitant procedures will be summarized separately from non-ophthalmic concomitant procedures. Ophthalmic concomitant procedures will be summarized for the study eye and fellow eye separately.

7.3. Study Treatments

The study product vehicle, IMP and NIMP will be dispensed as detailed in the Schedule of Activities ([Appendix 13.1](#)).

A by-patient listing of study treatments will be presented and ordered by site.

7.3.1. Exposure and Compliance

The compliance for both the IMP and NIMP will be assessed by number CCI collected in eDiary.

Exposure and compliance to IMP

In treatment period, starting from the first IMP administration done at the baseline visit until the last expected administration, the IMP should be administered CCI (1 drop each time and three times per day). Compliance calculation is based on the number of administrations, CCI.

The duration (days) of exposure to the IMP will be calculated by using data collected in the eCRF as:

$$exposure\ IMP\ (days)_{eCRF} = last\ date\ of\ treatment_{eCRF} - first\ date\ of\ treatment_{eCRF} + 1$$

where first date of treatment and last date of treatment are derived from the dates collected in the eCRF in the Randomization and End of Treatment forms, respectively.

Compliance for the study eye will be derived on the period defined by the exposure (i.e. by using only data collected in the interval defined by first and last date / timepoint collected in the eCRF) as the proportion (%) between the actual number of administrations done in the study eye and the expected number of administrations done in the study eye. CCI

CCI

CCI

CCI

on

CCI

The actual number of administrations done in the study eye is derived by using data collected in the eDiary. CCI

Extra-administrations recorded in the eDiary between first and last administration date (timepoint not recorded in the eDiary) will be also included in the count if administered in the study eye. CCI

The compliance will then be derived as:

$$\text{compliance IMP} = 100 * \frac{\text{number of actual administration}_{e\text{Diary}}}{\text{expected number of administration}_{e\text{CRF}}}$$

Compliance will also be analyzed weekly from baseline to Week 4.

Gross non-compliance will be defined as accountability lower than 80% or greater than 120% and in case of gross non-compliance the patient will be excluded from the Per Protocol dataset.

Exposure and compliance to NIMP (ATs) in the follow-up period.

In follow-up period, the NIMP should be administered CCI each time and CCI per day) from V4 / Week 4 to V5 / Week 8. Compliance calculation is based on the number of administrations. CCI

The duration (days) of exposure to the NIMP will be calculated by using data collected in the eCRF as:

$$\begin{aligned} \text{exposure NIMP (days)}_{e\text{CRF}} \\ = \text{last administration date of NIMP}_{e\text{CRF}} - \text{date of first dispensing of NIMP}_{e\text{CRF}} + 1 \end{aligned}$$

where:

- last administration date of NIMP is derived from the date collected in the eCRF in the End of Study form
- date of first dispensing of NIMP is derived as the minimum among the dates of ATs dispensation that are recorded in Artificial Tears Dispensation form and Additional Dispensation form of the eCRF (since for subjects who discontinued IMP, ATs can be dispensed in advance respect to V4 / Week 4).

Compliance for the study eye will be derived for the follow-up period only as the proportion (%) between the actual number of administrations done in the study eye and the expected number of administrations done in the study eye. CCI

The expected number of CCI in the study eye is derived as follows:

CCI

The actual number of administrations in the study eye is derived by using data collected in the eDiary, planned for the follow-up phase. Only administrations done in the period defined by the exposure to NIMP (extremes included) will be used in the calculation. Extra-administrations recorded in the eDiary in the same period will be also included in the count if administered in the study eye. Any extra-administration is collected in the study eDiary at the following question “How many extra doses of the artificial tears today?”. (e.g. if the answer is “4”, then 4 additional administrations will be added in the count of actual administrations).

The compliance will then be derived as:

$$\text{compliance NIMP} = 100 * \frac{\text{number of actual administration}_{e\text{Diary}}}{\text{expected number of administration}_{e\text{CRF}}}$$

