11.6 QUALITY TOLERANCE LIMITS

Gross noncompliance (see § 6.5 for derivation of compliance by using the number of drops collected in the diary) will be defined as compliance lower than 80% or greater than 120% and in case of gross noncompliance the patient will be excluded from the Per Protocol dataset. Quality tolerance limits are indicated in the centralized monitoring plan.

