4.3.5. Per-Protocol Population (PP)

The Per Protocol (PP) population will consist of all patients in the FAS population who do not have major protocol deviations. Primary efficacy analysis will be conducted on the FAS population while SAF and PP populations will be used for safety and sensitivity analysis, respectively.

Reasons for the exclusion from the PP will be determined in the masked Data Review Meeting. A non-exhaustive list of possible reasons for exclusion from the PP can be found in [Section 5.2](#).

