7.3.2. Accountability

Accountability for the IMP will be made by determining the number of Study Product vials dispensed to the patient at Day1/Baseline/V2 and at Week 2/V3 and the number of unused study medication vials returned at Week 2/V3, Week 4/V4 (EOT) Week 8/Follow-up (EOS)/V5. Accountability will be evaluated according to the following formula:

$$\text{Accountability} = 100 * \frac{(\text{number of vials dispensed}) - (\text{number of unused vials returned})}{\text{total number of vials dispensed}}$$

Below calculations will be done for treatment period and follow-up period separately to assess the accountability for IMP.

Number of vials dispensed refers to the total dispensed vials of Study Product as per the protocol up to the last date of specific study product administration. The number of vials of Study Product in each kit dispensed is **C** per protocol. Thus, the total number of vials dispensed would be calculated by number of kits dispensed multiplied by **C**.

Number of unused vials returned refers to the total unused vials of Study Product returned, over the duration for which the patient is on the treatment period.

Patient level listings of all study products administered along with reasons not dispensed study products will be provided.

The SAF, where treatment assignment is according to the actual treatment received, will be used for all summaries and listings of exposure and compliance to the study treatment. Accountability will be listed based on the SAF only.

8. Efficacy Analysis

Unless otherwise specified, all efficacy analyses with statistical hypothesis testing performed and descriptive analyses will be analyzed for the study eye only. Assessments collected for the fellow eye will be presented in listings only.

Unless otherwise specified, descriptive statistics will be used to summarize efficacy assessments for study eye at each scheduled visit. Change from baseline values for quantitative variables and shift from baseline for qualitative variables will be summarized for all available post-baseline visits by means of descriptive statistics.

CCI

All collected assessments will be presented in by-patient listings by treatment arm and ordered by site.

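### SAP 7.3.1 ties Per Protocol exclusion to vial accountability, contradicting the diary-compliance rule in SAP 5.2 and Protocol 11.6; its upper limit can never be reached

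*SAP*

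**What the plan says.** Four places bear on who leaves the PP set for poor adherence to the investigational product (IMP).

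- **SAP 7.3.1 (Exposure and Compliance)** builds a diary measure: "The actual number of administrations done in the study eye is derived by using data collected in the eDiary". That count, including extra administrations in the study eye, is divided by the expected number. The rule that follows uses a different term: "Gross non-compliance will be defined as accountability lower than 80% or greater than 120" (percent). Patients meeting it are excluded from the PP dataset.
- **SAP 7.3.2 (Accountability)** defines that term from vials: "Accountability will be evaluated according to the following formula". The formula is dispensed minus unused returned, divided by dispensed. The section closes by limiting accountability to a listing in the safety population.
- **SAP 5.2 (Protocol Deviations)** lists among the programmed major deviations "Lack of compliance with IMP (compliance <80% or compliance >120" (percent), and also "Exposure to IMP lower than expected (exposure in days < 24 days". The consequence is explicit: "Major PDs will define patients that will be excluded from the PP set".
- **Protocol 11.6 (Quality Tolerance Limits)** defines gross noncompliance "by using the number of drops collected in the diary) will be defined as compliance lower than 80% or greater than 120" (percent).

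The PP definition in SAP 4.3.5 sends the reader to SAP 5.2: "A non-exhaustive list of possible reasons for exclusion from the PP can be found in" that section.

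**The concern.** Two measures with the same 80% and 120% limits are each said to decide PP membership, and they measure different things. Diary compliance counts instillations. Accountability counts vials that did not come back unused. A vial serves one day whatever is taken from it (Protocol 6.3), so accountability does not register skipped drops within a day, and an unused vial that is never returned counts as used. An upper limit on a ratio that cannot exceed 100% also has no function.

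At stake is the PP analysis of the primary endpoint, one of the sensitivity analyses in SAP 8.1.2. If its membership rule can be read in two ways, two programmers could produce two PP sets from the same data. Quoting the protocol does not settle this: the SAP introduction gives the SAP precedence over the protocol, and the conflict is also internal to the SAP.

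**Working it through.** **Inputs**

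- 14 daily boxes per biweekly kit, one product vial each (Protocol 6.3). Two kits cover the treatment period, so 2 × 14 = 28 vials. The SAP's vials-per-kit figure is redacted.
- Up to 84 expected drops in the study eye (Protocol 6.5). The SAP's text on expected administrations is redacted.
- Accountability = 100 × (dispensed − unused returned) / dispensed (SAP 7.3.2).
- Diary compliance = 100 × actual administrations / expected administrations (SAP 7.3.1).

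**Step 1. Reproduce the plan's own figure.** 28 days × 3 drops = 84, as the protocol states.

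**Step 2. Range of accountability.** With 0 to 28 vials returned unused, it runs from 28/28 = 100% down to 0/28 = 0%. It cannot pass 100% for any kit size, because the number returned cannot be negative. The upper limit is never met. The lower limit is met from 6 vials returned: 22/28 = 78.6%, while 5 returned gives 23/28 = 82.1%.

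**Step 3. Range of diary compliance.** On 84 expected drops both limits work: 67 drops is 79.8% (excluded), 68 is 81.0% (kept), 100 is 119.0% (kept) and 101 is 120.2% (excluded).

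**Step 4. Compare the two rules.**

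| Patient | Diary compliance | Accountability | SAP 5.2 compliance rule | SAP 7.3.1 sentence |
|---|---|---|---|---|
| One drop a day, vial opened daily, 28 days | 28/84 = 33.3% | 28/28 = 100% | excluded | not flagged |
| Two drops a day, vial opened daily, 28 days | 56/84 = 66.7% | 100% | excluded | not flagged |
| Full dosing on 14 of 28 days, no unused vials returned | 42/84 = 50.0% | 100% | excluded | not flagged |
| Over-use, 101 drops from 28 vials | 120.2% | 100% | excluded | not flagged |
| Full dosing on 22 of 28 days, 6 vials returned | 66/84 = 78.6% | 22/28 = 78.6% | excluded | excluded |
| 27 treatment days, full dosing on 22, 6 vials returned | 66/81 = 81.5% | 22/28 = 78.6% | kept | excluded |

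The last row assumes three expected drops per exposure day, so 27 × 3 = 81. Twenty-seven days is within the Visit 4 window and above the 24-day exposure floor.

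**Step 5. Combine the rules.** Both statements are exclusions, and neither restores a patient whom the other removes. Applied together, the first four patients leave under SAP 5.2 and the fifth leaves under either rule. The only effect of the 7.3.1 sentence is to remove the sixth as well. Applied alone, 7.3.1 leaves the first four in.

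**Step 6. How easily does the extra removal arise?** On a fixed 84-drop denominator, with whole days skipped, every unused vial returned and no extra drops, the two measures agree, as in the fifth row. They separate in this direction when the denominator is shorter than 84 or when extra administrations lift the diary count. For example, 66 + 2 = 68 drops gives 68/84 = 81.0% against 78.6% accountability. The group is real but narrow.

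**The case against.** The strongest reply is that this is a slip of one noun. The sentence sits in the compliance section, directly after the compliance formula, with the limits used in SAP 5.2 and Protocol 11.6. SAP 7.3.2 says accountability is only listed. Protocol section 13 gives, as the reason for revising 11.6, that compliance was aligned throughout on drops recorded in the diary. The PP definition points to SAP 5.2, which excludes on diary compliance. Exclusions are settled at a masked data review meeting, so the conflict can be resolved before unmasking.

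Most of this stands. A reader might infer from 7.3.1 that the SAP has replaced diary compliance with vial accountability, and that the PP set therefore keeps gross under-dosers and can never exclude over-users. The documents do not support that. SAP 5.2 makes both kinds of patient major deviators, and nothing in 7.3.1 retains a patient because accountability is acceptable. Section 7.3.1 itself measures over-use, since it counts extra administrations; only the flagging sentence uses the wrong term.

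The reply does not make the sentence harmless. It is worded as an unconditional exclusion, and SAP 4.3.5 calls the list in 5.2 non-exhaustive. A programmer could properly treat 7.3.1 as an additional rule and remove patients whom 5.2 keeps.

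**Conclusion.** SAP 7.3.1 is wrong as written. It is a minor internal contradiction with SAP 5.2, SAP 7.3.2 and Protocol 11.6. Its 120% limit is void for any kit size, and its 80% limit does not detect partial daily dosing from opened vials.

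The effect depends on how the text is programmed. With both rules, the PP set can only lose further patients, namely those with adequate diary compliance but about 6 or more of 28 vials returned unused. With 7.3.1 alone, under-dosers and over-users would be missed. With SAP 5.2 alone, the result is what the protocol describes. The documents give no basis for estimating how many patients would be affected.

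The reach is limited to PP membership and the PP sensitivity analysis. The primary analysis uses the Full Analysis Set and is untouched.

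The vial counts rest on 14 vials per kit, and the drop counts on 84 expected drops, both taken from the protocol. The 27-day example also assumes three expected drops per exposure day. The contradiction and the 100% cap need none of these figures.

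**What to change.** In the gross non-compliance sentence of SAP 7.3.1, replace *accountability* with *compliance*, meaning diary administrations divided by expected administrations as derived in that section. This matches SAP 5.2 and Protocol 11.6 and makes both limits operable. SAP 7.3.2 needs no change, since it already confines accountability to listings.

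The cost is a one-word SAP correction. It needs no new data and no protocol amendment, and it should be made before the masked data review meeting fixes the PP set.
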